## 10. Final Power Assessment

Date conducted: 4/15/2021

Re-calculate power in the appropriate excel table, using the revised number of matched patients from the PS-match in Section 9. All other parameters in the table should be the same as in Section 8.

- Pooled

Superiority Analysis	
Number of patients matched	3,774
Reference	1,887
Exposed	1,887
Risk per 1,000 patients	25.12
Desired HR from RCT	0.49
Alpha (2-sided)	0.05
Number of events expected	94.80288
Power	0.93484302

- Optum CDM

Superiority Analysis	
Number of patients matched	1,092
Reference	546
Exposed	546
Risk per 1,000 patients	25.28
Desired HR from RCT	0.49
Alpha (2-sided)	0.05
Number of events expected	27.60576
Power	0.465815489

- IBM® MarketScan®

Superiority Analysis	
Number of patients matched	830
Reference	415
Exposed	415
Risk per 1,000 patients	12.77
Desired HR from RCT	0.49
Alpha (2-sided)	0.05
Number of events expected	10.5991
Power	0.21311438

- CMS - Diabetes

Superiority Analysis	
Number of patients matched	1,852
Reference	926
Exposed	926
Risk per 1,000 patients	31.17
Desired HR from RCT	0.49
Alpha (2-sided)	0.05
Number of events expected	57.72684
Power	0.773370349

- Stop analyses until balance and final power assessment are reviewed by primary investigators, FDA, and assigned members of advisory board.

Reviewed by PI:		Date reviewed:	
Reviewed by FDA:		Date reviewed:	
Reasons for stopping analysis (if required):			

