### 1.4 Required power for primary endpoint and noninferiority margin (if applicable)

Based on prior literature, it was determined that 66 MACE events and 876 subjects would be required to reject a two-sided null hypothesis of equal hazards with 80% power at a 5% type I error rate. A hazard ratio of 0.49 with absolute event rates of 5.1% and 10.2% (degarelix vs leuprolide) were hypothesized.

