CENSORING REASONS FOR STUDY OUTCOME			
Reasons	Optum CDM	IBM® MarketScan®	CMS - Diabetes
Outcome	108 (2.5%)	43 (1.3%)	211 (3.1%)
Start of an additional exposure	351 (8.2%)	256 (7.6%)	584 (8.6%)
End of index exposure	3,344 (78.3%)	2,674 (79.4%)	5,277 (78.0%)
Maximum follow-up time	118 (2.8%)	94 (2.8%)	205 (3.0%)
Specified date reached	182 (4.3%)	52 (1.5%)	270 (4.0%)
End of patient data	0 (0.0%)	0 (0.0%)	0 (0.0%)
End of patient enrollment	169 (4.0%)	248 (7.4%)	222 (3.3%)

- Report overall risk of the primary outcome.

	Optum CDM	IBM® MarketScan®	CMS - Diabetes	Pooled
Risk per 1,000 patients	25.28	12.77	31.17	25.12

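### Sections 8 and 10 apply the overall risk of an 86% leuprolide cohort to a 50:50 matched cohort while assuming HR 0.49; expected events are about 25% too high and pooled power is about 87%, not 93.5%

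*Combined protocol and SAP*

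**What the plan says.** Section 7 asks the team to "Report overall risk of the primary outcome" and bars event rates by treatment group. The pooled result is 25.12 per 1,000, from a cohort of 12,440 leuprolide and 1,968 degarelix patients.

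Section 8 multiplies that risk by the total number of 1:1 matched patients. Section 10 repeats the calculation after the full propensity-score match, with the instruction "All other parameters in the table should be the same as in Section 8". Its pooled table reads "Number of patients matched 3,774", "Risk per 1,000 patients 25.12", "Desired HR from RCT 0.49", "Alpha (2-sided) 0.05" and "Number of events expected 94.80288", with power 0.93484302.

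Section 1.4 shows that this hazard ratio stands for clearly unequal arm risks in the trial being emulated: "A hazard ratio of 0.49 with absolute event rates of 5.1% and 10.2% (degarelix vs leuprolide) were hypothesized".

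**The concern.** The overall risk is an average over a mix that is 86% leuprolide and 14% degarelix. Matching changes the mix to 50:50. Under HR 0.49 the average must then fall, because more of the patients are in the lower-risk arm. The tables keep it unchanged, so the same table assumes both a large treatment effect and an event count that is compatible only with a higher underlying risk than the one observed.

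When the assumed HR is below 1, the source cohort is mostly comparator and the arms are otherwise alike, this mistake overstates events and power. Both sections stop the work until the investigators, FDA and advisory board have looked at these numbers, and the confidence vote in Section 11 follows. A power figure used in that way should agree with its own assumptions.

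**Working it through.** **Inputs.** Leuprolide and degarelix counts (Section 7): Optum 3,676 and 596; MarketScan 2,936 and 431; CMS 5,828 and 941. Events: 108, 43 and 211, total 362. Overall risks per 1,000: 25.28, 12.77 and 31.17; pooled 362/14,408 = 25.12. Matched pairs (Section 10): 546, 415 and 926; pooled 1,887. HR 0.49 and two-sided alpha 0.05.

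**Reproducing the plan.** Events d = 3,774 × 0.02512 = 94.80. With the Schoenfeld formula for 1:1 allocation, power = Φ(√(d/4) × |ln 0.49| − 1.96) plus the negligible opposite tail. Here √(94.80/4) × 0.7133 − 1.96 = 1.513, and Φ(1.513) = 0.9348, as stated. The same formula reproduces all the database-level powers in Sections 8 and 10, so the method is not in doubt.

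**Making the inputs consistent.** Let r be the leuprolide risk, and let the degarelix risk be 0.49r. The observed average fixes r:

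- Weights: 12,440/14,408 = 0.8634 and 1,968/14,408 = 0.1366.
- r = 25.12 / (0.8634 + 0.49 × 0.1366) = 25.12 / 0.9303 = 27.00 per 1,000.
- Degarelix risk: 0.49 × 27.00 = 13.23 per 1,000.
- Expected events: 1,887 × (27.00 + 13.23)/1,000 = 75.9.
- Power: √(75.9/4) × 0.7133 − 1.96 = 1.148, which gives 87.4%.

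The stated event count is 94.8/75.9 = 1.25 times the consistent one. The same steps with each database's own weights and risk give:

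| Table | Events stated | Events consistent | Power stated | Power consistent |
|---|---|---|---|---|
| Final, pooled | 94.8 | 75.9 | 93.5% | 87.4% |
| Final, CMS | 57.7 | 46.3 | 77.3% | 68.0% |
| Final, Optum | 27.6 | 22.1 | 46.6% | 38.9% |
| Final, MarketScan | 10.6 | 8.4 | 21.3% | 17.9% |
| Initial, pooled | 98.8 | 79.1 | 94.4% | 88.7% |

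Adding the three database-specific final counts instead of using one pooled r gives 76.9 events and 87.8% power.

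**Cross-check in reverse.** To get 94.8 events from 1,887 pairs at HR 0.49, the leuprolide risk must be 94.80/(1,887 × 1.49) = 33.7 per 1,000 and the degarelix risk 16.5. In the unmatched cohort those risks would give 12,440 × 0.0337 + 1,968 × 0.0165 ≈ 452 events. Section 7 reports 362.

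**The case against.** **The multiplication is correct.** True: each stated figure follows from its inputs. The fault is that the inputs do not fit together.

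**Matching may select higher-risk leuprolide patients.** The correction takes the two groups to have the same baseline risk, and before matching they differed. Pooled prostate cancer comorbidity index was 35.44 on leuprolide against 36.38 on degarelix, smoking 25.1% against 28.5%, and no prostate imaging 47.9% against 34.7%. The documents do not translate these differences into MACE risk. If degarelix-type patients had a baseline risk 5%, 10% or 20% higher (an assumption), pooled events would be 79.4, 82.9 or 89.8 and power 88.9%, 90.1% or 92.2%. It would take about 27% to restore 94.8 events. The plan makes no such argument and carries the unmatched risk forward as it is.

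**Follow-up differs by arm.** In Section 7 the degarelix medians are shorter (67 to 82 days against 89), but the upper quartiles are longer (124 to 132 against 89), and means are not given. Varying degarelix follow-up from 0.7 to 1.3 times that of leuprolide (an assumption) gives 69.9 to 81.6 events and 84.7% to 89.7% power. Restoring the stated count would need a factor of 1/0.49, about 2.04, which simply cancels the assumed effect.

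**The consequence is limited.** This stands. Pooled power stays above 80%, and 75.9 events exceed both the 66 that the trial required (Section 1.4) and the 62 that Schoenfeld gives for 80% power. Every single database is below 80% with or without the correction, and the plan sets no power threshold for proceeding.

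**Conclusion.** The point holds, and the power tables are wrong as written. The overall risk and the HR of 0.49 cannot both apply to the matched cohort in the way the tables use them, and no section adjusts for the change from 86:14 to 50:50. Consistent inputs put final pooled power at about 87% on about 76 events. CMS, the only database near 80%, drops to 68%.

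The estimate assumes that risk scales with the hazard ratio at these low risks, that follow-up and baseline risk are similar in the two arms, and that matching does not change the underlying risk. The size moves with these assumptions, but the direction survives any modest departure from them. The study does not become underpowered in the pooled analysis; the reported margin is smaller than reviewers are told.

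**What to change.** In Sections 8 and 10, replace matched N × overall risk with n_ref × r + n_exp × 0.49 × r, where r = overall risk / (w_leuprolide + 0.49 × w_degarelix) and the weights are the unmatched arm shares from Section 7. Do this in each database. For the pooled row, say whether one pooled r is used (75.9 events, 87.4%) or the database counts are added (76.9 events, 87.8%). Remove the Section 10 instruction to carry the risk over unchanged, state the equal-baseline-risk and equal-follow-up assumptions, and add a short sensitivity range such as the ones above.

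The cost is one spreadsheet formula and a less favourable power figure. No patients are added. No event rates by treatment are needed, so the blinding in Section 7 is kept. The Section 10 review fields carry no dates in this version, so the tables can apparently still be restated before sign-off.

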## 11. Study Confidence and Concerns

Deadline for voting on study confidence and listing concerns:

Date votes and concerns are summarized:

- If final feasibility and power analyses are reviewed and approved, proceed to the remaining protocol steps.

- All study team and advisory board members that review this protocol should at this stage provide their level of confidence for the success of the RWD study in the [Google Form](#). This form also provides space for reviewers to list any concerns that they feel may contribute to a failure to replicate the findings of the RCT, including differences in study populations, poor measurement of study variables, or residual confounding. All responses will be kept confidential and individual-level results will only be shared with the individual respondent.
- After the deadline for voting has passed, provide the distribution of responses and summarize all concerns here.

## **12. Register study protocol on clinicalTrials.gov**

Date conducted:

- Register the study on [clinicalTrials.gov](#) and upload this document.

## **13. Comparative Analyses**

Action report name:

Date conducted:

13.1 For primary analysis:

13.2 For sensitivity analyses:

## **14. Requested Results**

14.1 Table 1: Baseline characteristics before and after adjustment

Variable	Before adjustment			After adjustment		
	Referent	Exposure	Std. diff.	Referent	Exposure	Std. diff.
Number of patients			-			-
Age categories						
...						

14.2 Table 2: Follow-up time

Patient Group	Median Follow-Up Time (Days) [IQR]
Overall Patient Population	
Referent	
Exposure	

14.3 Table 3: Censoring events

	Overall	Referent	Exposure
Outcome			
Death			
Start of an additional exposure			
End of index exposure			
Specified date reached			
End of patient data			
End of patient enrollment			
...			

14.4 Table 4: Results from primary analyses;

Analysis	No. exposed events	No. referent events	Exposed rate	Referent rate	HR (95% CI)
Crude					
Analysis 1					
Analysis 2					
...					

HR, Hazard Ratio; CI, Confidence Interval.

14.5 Table 5: Results from secondary analyses;

## Appendix A

### Information from Trial

Trial Name: PRONOUNCE <https://www.clinicaltrials.gov/ct2/show/NCT02663908>

NCT: NCT02663908

Therapeutic Area: Oncology

RCT Category: Equivalence/Superiority

Brand Name: Firmagon

Generic Name: Degarelix

Sponsor: Ferring Pharmaceuticals

Year: 2016 - Present

Measurable Endpoint: MACE

Exposure: Degarelix

Comparator: Leuprolide

Population: Men of any age with with advance prostate cancer and predefined CV disease

No. of Patients: TBD

Power: TBD

1 Histologically confirmed adenocarcinoma of the prostate	Measured from [start of all available data, 0]. Must have both diagnosis code and male gender for inclusion. Malignant Neoplasm of the Prostate ICD-9 diagnosis: 188.0-188.9 ICD-10 diagnosis: C61.0 (inpatient and outpatient) Sex: Male		Male patients with ICD-9 - an exposure provides enough information to confirm diagnosis, as the exposures have very few or no indications outside of advanced PC	
2 Tumor, node, metastasis staging available before treatment start (bone scan and/or CT scan and/or MRI) <12 weeks before study start			Necessitating code for biopsy may exclude subjects with apparent prostate cancer if they were initially diagnosed prior to database enrollment with early stage disease	
3 Investigator judgement to initiate combined ADT therapy with intended duration of 12 months or longer			Lupron is indicated in females for endometriosis. Restricting to males helps ensure indication of interest.	
4 Patients with prostate cancer who developed metastases after local therapy				
5 -Patients with prostate cancer with very high-risk, high-risk, or intermediate risk disease with feature of unfavorable prognosis who will be treated with definitive radiation therapy in combination with at least 12 months of neoadjuvant/adjacent ADT				
		Measured from [start of all available data, 30] on an inpatient or outpatient care setting in any diagnosis position		
		Acute or old MI: ICD-9 diagnosis: 410.xx, 412.xx ICD-10 diagnosis: I21.00-I21.09, I21.10-I21.19, I21.21, I21.29, I21.3, I21.4, I22.0, I22.1, I22.2, I22.8, I22.9, I25.2		
		Coronary, Carotid, Iliac, Femoral, Popliteal revascularization (angioplasty/Stent/CABG/vascular bypass/endarterectomy): ICD-9 procedure: "36.67", "36.69", "36.07", "36.09", "36.31", "36.32", "36.33", "36.34", "36.17", "36.10", "36.11", "36.12", "36.13", "36.14", "36.15", "36.16", "36.17", "36.18", "36.2", "36.21", "36.22", "36.23", "36.24", "36.25", "36.26", "36.27", "36.28", "36.29", "36.30", "36.31", "36.32", "36.33", "36.34", "36.35", "36.36", "36.37", "36.38", "36.39", "36.40", "36.41", "36.42", "36.43", "36.44", "36.45", "36.46", "36.47", "36.48", "36.49", "36.50", "36.51", "36.52", "36.53", "36.54", "36.55", "36.56", "36.57", "36.58", "36.59", "36.60", "36.61", "36.62", "36.63", "36.64", "36.65", "36.66", "36.67", "36.68", "36.69", "36.70", "36.71", "36.72", "36.73", "36.74", "36.75", "36.76", "36.77", "36.78", "36.79", "36.80", "36.81", "36.82", "36.83", "36.84", "36.85", "36.86", "36.87", "36.88", "36.89", "36.90", "36.91", "36.92", "36.93", "36.94", "36.95", "36.96", "36.97", "36.98", "36.99", "36.100", "36.101", "36.102", "36.103", "36.104", "36.105", "36.106", "36.107", "36.108", "36.109", "36.110", "36.111", "36.112", "36.113", "36.114", "36.115", "36.116", "36.117", "36.118", "36.119", "36.120", "36.121", "36.122", "36.123", "36.124", "36.125", "36.126", "36.127", "36.128", "36.129", "36.130", "36.131", "36.132", "36.133", "36.134", "36.135", "36.136", "36.137", "36.138", "36.139", "36.140", "36.141", "36.142", "36.143", "36.144", "36.145", "36.146", "36.147", "36.148", "36.149", "36.150", "36.151", "36.152", "36.153", "36.154", "36.155", "36.156", "36.157", "36.158", "36.159", "36.160", "36.161", "36.162", "36.163", "36.164", "36.165", "36.166", "36.167", "36.168", "36.169", "36.170", "36.171", "36.172", "36.173", "36.174", "36.175", "36.176", "36.177", "36.178", "36.179", "36.180", "36.181", "36.182", "36.183", "36.184", "36.185", "36.186", "36.187", "36.188", "36.189", "36.190", "36.191", "36.192", "36.193", "36.194", "36.195", "36.196", "36.197", "36.198", "36.199", "36.100", "36.101", "36.102", "36.103", "36.104", "36.105", "36.106", "36.107", "36.108", "36.109", "36.110", "36.111", "36.112", "36.113", "36.114", "36.115", "36.116", "36.117", "36.118", "36.119", "36.120", "36.121", "36.122", "36.123", "36.124", "36.125", "36.126", "36.127", "36.128", "36.129", "36.130", "36.131", "36.132", "36.133", "36.134", "36.135", "36.136", "36.137", "36.138", "36.139", "36.140", "36.141", "36.142", "36.143", "36.144", "36.145", "36.146", "36.147", "36.148", "36.149", "36.150", "36.151", "36.152", "36.153", "36.154", "36.155", "36.156", "36.157", "36.158", "36.159", "36.160", "36.161", "36.162", "36.163", "36.164", "36.165", "36.166", "36.167", "36.168", "36.169", "36.170", "36.171", "36.172", "36.173", "36.174", "36.175", "36.176", "36.177", "36.178", "36.179", "36.180", "36.181", "36.182", "36.183", "36.184", "36.185", "36.186", "36.187", "36.188", "36.189", "36.190", "36.191", "36.192", "36.193", "36.194", "36.195", "36.196", "36.197", "36.198", "36.199", "36.100", "36.101", "36.102", "36.103", "36.104", "36.105", "36.106", "36.107", "36.108", "36.109", "36.110", "36.111", "36.112", "36.113", "36.114", "36.115", "36.116", "36.117", "36.118", "36.119", "36.120", "36.121", "36.122", "36.123", "36.124", "36.125", "36.126", "36.127", "36.128", "36.129", "36.130", "36.131", "36.132", "36.133", "36.134", "36.135", "36.136", "36.137", "36.138", "36.139", "36.140", "36.141", "36.142", "36.143", "36.144", "36.145", "36.146", "36.147", "36.148", "36.149", "36.150", "36.151", "36.152", "36.153", "36.154", "36.155", "36.156", "36.157", "36.158", "36.159", "36.160", "36.161", "36.162", "36.163", "36.164", "36.165", "36.166", "36.167", "36.168", "36.169", "36.170", "36.171", "36.172", "36.173", "36.174", "36.175", "36.176", "36.177", "36.178", "36.179", "36.180", "36.181", "36.182", "36.183", "36.184", "36.185", "36.186", "36.187", "36.188", "36.189", "36.190", "36.191", "36.192", "36.193", "36.194", "36.195", "36.196", "36.197", "36.198", "36.199", "36.100", "36.101", "36.102", "36.103", "36.104", "36.105", "36.106", "36.107", "36.108", "36.109", "36.110", "36.111", "36.112", "36.113", "36.114", "36.115", "36.116", "36.117", "36.118", "36.119", "36.120", "36.121", "36.122", "36.123", "36.124", "36.125", "36.126", "36.127", "36.128", "36.129", "36.130", "36.131", "36.132", "36.133", "36.134", "36.135", "36.136", "36.137", "36.138", "36.139", "36.140", "36.141", "36.142", "36.143", "36.144", "36.145", "36.146", "36.147", "36.148", "36.149", "36.150", "36.151", "36.152", "36.153", "36.154", "36.155", "36.156", "36.157", "36.158", "36.159", "36.160", "36.161", "36.162", "36.163", "36.164", "36.165", "36.166", "36.167", "36.168", "36.169", "36.170", "36.171", "36.172", "36.173", "36.174", "36.175", "36.176", "36.177", "36.178", "36.179", "36.180", "36.181", "36.182", "36.183", "36.184", "36.185", "36.186", "36.187", "36.188", "36.189", "36.190", "36.191", "36.192", "36.193", "36.194", "36.195", "36.196", "36.197", "36.198", "36.199", "36.100", "36.101", "36.102", "36.103", "36.104", "36.105", "36.106", "36.107", "36.108", "36.109", "36.110", "36.111", "36.112", "36.113", "36.114", "36.115", "36.116", "36.117", "36.118", "36.119", "36.120", "36.121", "36.122", "36.123", "36.124", "36.125", "36.126", "36.127", "36.128", "36.129", "36.130", "36.131", "36.132", "36.133", "36.134", "36.135", "36.136", "36.137", "36.138", "36.139", "36.140", "36.141", "36.142", "36.143", "36.144", "36.145", "36.146", "36.147", "36.148", "36.149", "36.150", "36.151", "36.152", "36.153", "36.154", "36.155", "36.156", "36.157", "36.158", "36.159", "36.160", "36.161", "36.162", "36.163", "36.164", "36.165", "36.166", "36.167", "36.168", "36.169", "36.170", "36.171", "36.172", "36.173", "36.174", "36.175", "36.176", "36.177", "36.178", "36.179", "36.180", "36.181", "36.182", "36.183", "36.184", "36.185", "36.186", "36.187", "36.188", "36.189", "36.190", "36.191", "36.192", "36.193", "36.194", "36.195", "36.196", "36.197", "36.198", "36.199", "36.100", "36.101", "36.102", "36.103", "36.104", "36.105", "36.106", "36.107", "36.108", "36.109", "36.110", "36.111", "36.112", "36.113", "36.114", "36.115", "36.116", "36.117", "36.118", "36.119", "36.120", "36.121", "36.122", "36.123", "36.124", "36.125", "36.126", "36.127", "36.128", "36.129", "36.130", "36.131", "36.132", "36.133", "36.134", "36.135", "36.136", "36.137", "36.138", "36.139", "36.140", "36.141", "36.142", "36.143", "36.144", "36.145", "36.146", "36.147", "36.148", "36.149", "36.150", "36.151", "36.152", "36.153", "36.154", "36.155", "36.156", "36.157", "36.158", "36.159", "36.160", "36.161", "36.162", "36.163", "36.164", "36.165", "36.166", "36.167", "36.168", "36.169", "36.170", "36.171", "36.172", "36.173", "36.174", "36.175", "36.176", "36.177", "36.178", "36.179", "36.180", "36.181", "36.182", "36.183", "36.184", "36.185", "36.186", "36.187", "36.188", "36.189", "36.190", "36.191", "36.192", "36.193", "36.194", "36.195", "36.196", "36.197", "36.198", "36.199", "36.100", "36.101", "36.102", "36.103", "36.104", "36.105", "36.106", "36.107", "36.108", "36.109", "36.110", "36.111", "36.112", "36.113", "36.114", "36.115", "36.116", "36.117", "36.118", "36.119", "36.120", "36.121", "36.122", "36.123", "36.124", "36.125", "36.126", "36.127", "36.128", "36.129", "36.130", "36.131", "36.132", "36.133", "36.134", "36.135", "36.136", "36.137", "36.138", "36.139", "36.140", "36.141", "36.142", "36.143", "36.144", "36.145", "36.146", "36.147", "36.148", "36.149", "36.150", "36.151", "36.152", "36.153", "36.154", "36.155", "36.156", "36.157", "36.158", "36.159", "36.160", "36.161", "36.162", "36.163", "36.164", "36.165", "36.166", "36.167", "36.168", "36.169", "36.170", "36.171", "36.172", "36.173", "36.174", "36.175", "36.176", "36.177", "36.178", "36.179", "36.180", "36.181", "36.182", "36.183", "36.184", "36.185", "36.186", "36.187", "36.188", "36.189", "36.190", "36.191", "36.192", "36.193", "36.194", "36.195", "36.196", "36.197", "36.198", "36.199", "36.100", "36.101", "36.102", "36.103", "36.104", "36.105", "36.106", "36.107", "36.108", "36.109", "36.110", "36.111", "36.112", "36.113", "36.114", "36.115", "36.116", "36.117", "36.118", "36.119", "36.120", "36.121", "36.122", "36.123", "36.124", "36.125", "36.126", "36.127", "36.128", "36.129", "36.130", "36.131", "36.132", "36.133", "36.134", "36.135", "36.136", "36.137", "36.138", "36.139", "36.140", "36.141", "36.142", "36.143", "36.144", "36.145", "36.146", "36.147", "36.148", "36.149", "36.150", "36.151", "36.152", "36.153", "36.154", "36.155", "36.156", "36.157", "36.158", "36.159", "36.160", "36.161", "36.162", "36.163", "36.164", "36.165", "36.166", "36.167", "36.168", "36.169", "36.170", "36.171", "36.172", "36.173", "36.174", "36.175", "36.176", "36.177", "36.178", "36.179", "36.180", "36.181", "36.182", "36.183", "36.184", "36.185", "36.186", "36.187", "36.188", "36.189", "36.190", "36.191", "36.192", "36.193", "36.194", "36.195", "36.196", "36.197", "36.198", "36.199", "36.100", "36.101", "36.102", "36.103", "36.104", "36.105", "36.106", "36.107", "36.108", "36.109", "36.110", "36.111", "36.112", "36.113", "36.114", "36.115", "36.116", "36.117", "36.118", "36.119", "36.120", "36.121", "36.122", "36.123", "36.124", "36.125", "36.126", "36.127", "36.128", "36.129", "36.130", "36.131", "36.132", "36.133", "36.134", "36.135", "36.136", "36.137", "36.138", "36.139", "36.140", "36.141", "36.142", "36.143", "36.144", "36.145", "36.146", "36.147", "36.148", "36.149", "36.150", "36.151", "36.152", "36.153", "36.154", "36.155", "36.156", "36.157", "36.158", "36.159", "36.160", "36.161", "36.162", "36.163", "36.164", "36.165", "36.166", "36.167", "36.168", "36.169", "36.170", "36.171", "36.172", "36.173", "36.174", "36.175", "36.176", "36.177", "36.178", "36.179", "36.180", "36.181", "36.182", "36.183", "36.184", "36.185", "36.186", "36.187", "36.188", "36.189", "36.190", "36.191", "36.192", "36.193", "36.194", "36.195", "36.196", "36.197", "36.198", "36.199", "36.100", "36.101", "36.102", "36.103", "36.104", "36.105", "36.106", "36.107", "36.108", "36.109", "36.110", "36.111", "36.112", "36.113", "36.114", "36.115", "36.116", "36.117", "36.118", "36.119", "36.120", "36.121", "36.122", "36.123", "36.124", "36.125", "36.126", "36.127", "36.128", "36.129", "36.130", "36.131", "36.132", "36.133", "36.134", "36.135", "36.136", "36.137", "36.138", "36.139", "36.140", "36.141", "36.142", "36.143", "36.144", "36.145", "36.146", "36.147", "36.148", "36.149", "36.150", "36.151", "36.152", "36.153", "36.154", "36.155", "36.156", "36.157", "36.158", "36.159", "36.160", "36.161", "36.162", "36.163", "36.164", "36.165", "36.166", "36.167", "36.168", "36.169", "36.170", "36.171", "36.172", "36.173", "36.174", "36.175", "36.176", "36.177", "36.178", "36.179", "36.180", "36.181", "36.182", "36.183", "36.184", "36.185", "36.186", "36.187", "36.188", "36.189", "36.190", "36.191", "36.192", "36.193", "36.194", "36.195", "36.196", "36.197", "36.198", "36.199", "36.100", "36.101", "36.102", "36.103", "36.104", "36.105", "36.106", "36.107", "36.108", "36.109", "36.110", "36.111", "36.112", "36.113", "36.114", "36.115", "36.116", "36.117", "36.118", "36.119", "36.120", "36.121", "36.122", "36.123", "36.124", "36.125", "36.126", "36.127", "36.128", "36.129", "36.130", "36.131", "36.132", "36.133", "36.134", "36.135", "36.136", "36.137", "36.138", "36.139", "36.140", "36.141", "36.142", "36.143", "36.144", "36.145", "36.146", "36.147", "36.148", "36.149", "36.150", "36.151", "36.152", "36.153", "36.154", "36		

[figure not shown]
[figure not shown]
[figure not shown]
